#### **TABLE 14.3.1.4:**

### Number and Percentage of Participants Experiencing Solicited Events by Severity, Day Post Vaccination and Treatment Group - Full Analysis Population

Continue for each symptom

TABLE 14.3.1.4(b) Any Local Reaction

TABLE 14.3.1.4(c) Pain at injection site

TABLE 14.3.1.4(d) Erythema at injection site

TABLE 14.3.1.4(e) Swelling at injection site

TABLE 14.3.1.4(f) Any Systemic Symptom

**TABLE 14.3.1.4(g) Fever** 

TABLE 14.3.1.4(h) Headache

TABLE 14.3.1.4(i) Fatigue/malaise

TABLE 14.3.1.4(j) Joint pain/arthralgia

TABLE 14.3.1.4(k) Muscle pain/myalgia

TABLE 14.3.1.4(l) Diarrhea

TABLE 14.3.1.4(m) Anorexia

[figure not shown]
**TABLE 14.3.1.4(n) Chills** 

TABLE 14.3.1.4(o) Vomiting

### FIGURE 14.3.1.5.1(a):

## Maximum Severity of Solicited Systemic Symptoms per Participant by Days Post Vaccination and Treatment Group - Full Analysis Population -Adjuvanted MCV-5

(N=XX)

### FIGURE 14.3.1.5.1(b):

Maximum Severity of Solicited Systemic Symptoms per Participant by Days Post Vaccination and Treatment Group - Full Analysis Population - Non-adjuvanted MCV-5

### FIGURE 14.3.1.5.1(c):

Maximum Severity of Solicited Systemic Symptoms per Participant by Days Post Vaccination and Treatment Group - Full Analysis Population - Menactra®

### FIGURE 14.3.1.5.2(a):

Maximum Severity of Solicited Local Reactions per Participant by
Days Post Vaccination and Treatment Group - Full Analysis Population - Adjuvanted MCV-5
(N=XX)

### FIGURE 14.3.1.5.2(b):

Maximum Severity of Solicited Local Reactions per Participant by Days Post Vaccination and Treatment Group - Full Analysis Population - Non-adjuvanted MCV-5

### **TABLE 14.3.1.8:**

Number and Percentage of Participants Experiencing Unsolicited Adverse Events Related to Study Product, by MedDRA® System Organ Class and Preferred Term, Maximum Severity, and Treatment Group - Full Analysis Population

Same format as Table 14.3.1.7

TABLE 14.3.1.9.1:

Number and Percentage of Participants Experiencing Unsolicited Adverse Events

by MedDRA® System Organ Class and Preferred Term, Days Post Vaccination and Treatment Group - Full Analysis Population

		A	Adjuvar	nted MCV	V -5	Non-a	adjuvant	ed MCV	7-5	C	ombined	MCV-5			Mena	ctra®	
MedDRA®	MedDRA®		s 1-8 =X)	Days (N=		Days (N=)		Day: (N=		Days (N=		Days (N=		_	vs 1-8 =X)	Day (N=	
System Organ Class	Preferred Term	n	%	N	%	n	%	n	%	n	%	n	%	n	%	n	%
Any SOC	Any PT																
[SOC 1]	Any PT																
	[PT 1]																
	[PT 2]																
[SOC 2]	Any PT																
	[PT 1]																
	[PT 2]																

Note: N=Number of participants in the Full Analysis population. For each time period, a participant is only counted once per preferred term and system organ class.

TABLE 14.3.1.9.2:

Number and Percentage of Participants Experiencing Related Unsolicited Adverse Events

by MedDRA® System Organ Class and Preferred Term, Days Post Vaccination and Treatment Group - Full Analysis Population

		A	Adjuvai	nted MCV	V -5	Non-a	ıdjuvant	ed MCV	7-5	C	ombined	MCV-5			Mena	ctra®	
MedDRA®	MedDRA®		s 1-8 =X)	Days (N=		Days (N=)		Days (N=		Days (N=		Days (N=		_	s 1-8 =X)	Day (N=	
System Organ Class	Preferred Term	n	%	N	%	n	%	n	%	n	%	n	%	n	%	n	%
Any SOC	Any PT																
[SOC 1]	Any PT																
	[PT 1]																
	[PT 2]																
[SOC 2]	Any PT																
	[PT 1]																
	[PT 2]																

[figure not shown]
Note: N=Number of participants in the Full Analysis population. For each time period, a participant is only counted once per preferred term and system organ class.

# TABLE 14.3.1.10: Number of Unsolicited Adverse Events by MedDRA® System Organ Class and Preferred Term, Days Post Vaccination and Treatment Group - Full Analysis Population

		Adjuvan	nted MCV-5	Non-adjuvant	ted MCV-5	Combined	MCV-5	Mena	ctra ®
MedDRA®	MedDRA®	Days 1-8 (N=X)	Days 8+ (N=X)						
System Organ Class	Preferred Term	# of Events	# of Events						
Any SOC	Any PT								
[SOC 1]	Any PT								
	[PT 1]								
	[PT 2]								
[SOC 2]	Any PT								
	[PT 1]								
	[PT 2]								

Note: N=Number of participants in the Full Analysis population. For each time period, a participant is only counted once per preferred term and system organ class.

FIGURE 14.3.1.11.1:
Proportion of Participants with Unsolicited, Non-Serious Adverse Events, by MedDRA® System
Organ Class and Maximum Severity per Participant - Full Analysis Population
- Adjuvanted MCV-5

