#### 8.7. Adverse Event Identification, Resolution and Reporting

To improve the quality and precision of acquired AE data, the PI should observe the following guidelines:

- Whenever possible, use recognized medical terms when recording AEs on the AE CRF. Do not use colloquialisms and/or abbreviations.
- If known, record the diagnosis (i.e., disease or syndrome) rather than component signs, symptoms and laboratory values on the AE CRF (e.g., record congestive heart failure rather than dyspnea, rales, and cyanosis). However, signs and symptoms that are considered unrelated to an encountered syndrome or disease should be recorded as individual AEs on the CRF (e.g., if congestive heart failure and severe headache are observed at the same time, each event should be recorded as an individual AE).

Page **55** of **106** 

AEs occurring secondary to other events (e.g., sequelae) should be identified by the
primary cause. A "primary" AE, if clearly identifiable, generally represents the most
accurate clinical term to record on the AE CRF. If a primary serious AE (SAE) is recorded
on an SAE CRF, events occurring secondary to the primary event should be described in
the narrative description of the case.

For example:

Orthostatic  $\rightarrow$  Fainting and  $\rightarrow$  Head  $\rightarrow$  Neck pain hypotension fall to floor trauma

The primary AE is orthostatic hypotension.

- Grade 2 or higher abnormal laboratory test results will be reported as AEs and assessed
  for severity according to severity grading criteria provided in Appendix II and causality
  (related or unrelated) to the study product. Grade 1 abnormal laboratory test results will
  be entered as AEs if the site PI determines them to be clinically significant.
- Death is an outcome of an event. The event that resulted in the death should be recorded and reported on the SAE CRF.
- For hospitalizations for surgical or diagnostic procedures, the illness leading to the surgical
  or diagnostic procedure should be recorded as the SAE, not the procedure itself. The
  procedure should be captured in the case narrative as part of the action taken in response
  to the illness.
- Pregnancies that occur in study participants are not considered AEs and will be recorded on a separate Pregnancy CRF. Pregnancy outcomes that include stillbirth and any congenital anomalies must be reported as SAEs.

AEs may be discovered through any of these methods.

- Observing the participant.

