#### 9.4 Adverse Events

All safety analyses will be presented using the FA population.

Any medical condition that is present at the time that the participant is screened will be considered baseline and not reported as an AE, unless it worsens in severity or increases in frequency during the study. A treatment-emergent adverse event is one that is observed after baseline or worsens in severity or increases in frequency during the study. Solicited and unsolicited adverse events (AEs) will be analyzed separately. When calculating the incidence of AEs (i.e., on a per participant basis), each participant will be counted once and any repetitions within a participant will be ignored; the denominator will be the total population size. For tables summarizing severity, the severity will be summarized as the maximum severity experienced by that participant for a particular AE or symptom. All adverse events reported will be included in the summaries and analyses.

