#### 9.4.3 Unsolicited Adverse Events

The proportion of participants reporting at least one unsolicited adverse event will be summarized by MedDRA® system organ class and preferred term for each treatment group and overall. Denominators for percentages are the number of participants in the FA population. A 95% CI calculated using Clopper-Pearson methodology from a binomial distribution (SAS PROC FREQ with a binomial option) will be presented for each MedDRA® system organ class and preferred term (Table 14.3.1.7)

Unsolicited adverse events by participant will be presented in Listing 16.2.7.2.

The following summaries for unsolicited adverse events will be presented by treatment group:

- Participant level summary of maximum severity and relationship to study product by MedDRA® SOC and PT (Table 14.3.1.8.1);
- Participant level summary of related unsolicited events by maximum severity, MedDRA® SOC and PT (Table 14.3.1.8.2);

- Participant incidence of unsolicited adverse events over time by MedDRA® SOC and PT (Days 1-8, Days > 8) (Table 14.3.1.9.1);
- Participant incidence of related unsolicited adverse events over time by MedDRA® SOC and PT (Days 1-8, Days > 8) (Table 14.3.1.9.2);
- Total frequency of adverse events over time by MedDRA® SOC and PT (Days 1-8, Days > 8) (Table 14.3.1.10);
- Participant listing of non-serious adverse events of moderate or greater severity (Table 14.3.2.2);
- Bar chart of the frequency of events for non-serious adverse events by maximum severity and MedDRA® SOC (Figure 14.3.1.11);

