### TABLE 14.3.2.2: Listing of Non-Serious, Unsolicited, Moderate or Severe Adverse Events

Participant ID	Treatment Group	Adverse Event	Start Date	# of Days Post Dose	Severity	Outcome	Resolution Date / Ongoing	Duration (Days)	Reasonable possibility that the study product caused the event?

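### SAP Table 14.3.1.10 is set up as an event count, but its footnote counts each participant once, so followed as written the plan has no true count of adverse events

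*SAP*

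**What the plan says.** **Table 14.3.1.10.** The shell is titled "Number of Unsolicited Adverse Events by MedDRA® System Organ Class and Preferred Term, Days Post Vaccination and Treatment Group", and its cells are headed as numbers of events. SAP 9.4.3 introduces it as "Total frequency of adverse events over time by" MedDRA system organ class (SOC) and preferred term (PT), split into Days 1-8 and later. The footnote reads: "For each time period, a participant is only counted once per preferred term and system organ class". The identical footnote is under Tables 14.3.1.9.1 and 14.3.1.9.2, which are titled as numbers and percentages of participants.

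**General rule.** SAP 9.4 states: "When calculating the incidence of AEs (i.e., on a per participant basis), each participant will be counted once". It then says that repetitions within a participant are ignored for that purpose. The rule is tied to incidence and is not stated for event totals.

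**Table 14.3.2.2.** SAP 9.4.3 describes it as "Participant listing of non-serious adverse events of moderate or greater severity". The shell's title is "Listing of Non-Serious, Unsolicited, Moderate or Severe Adverse Events". The severity scale in SAP 4.5.1.2 has a life-threatening Grade 4 above severe.

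**The concern.** An event total and a count of participants with at least one event are different quantities, and one table cannot be both. If the programmer follows the footnote, the cells are labelled as events but hold participants. A reader comparing Tables 14.3.1.9.1 and 14.3.1.10 would see equal figures and conclude that nobody had a repeat event, whatever the data show. Recurrence within a participant is useful information in a first-in-human vaccine study, and this is the one summary table designed to show it.

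Table 14.3.2.2 raises a smaller matter of the same kind. Its title stops at severe while the text has no upper limit. Protocol 8.7 states: "Grade 2 or higher abnormal laboratory test results will be reported as AEs". Seriousness under Protocol 8.3.2 depends on outcome or immediate risk of death, not on grade. A Grade 4 laboratory event can therefore be non-serious, and the title leaves it unclear whether it belongs in the listing.

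**Working it through.** The plan gives no figure to reproduce, so the check is mainly a comparison of texts.

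**1. Which instructions govern Table 14.3.1.10?**
- For counting events: the table title, the column heads, the description in SAP 9.4.3, and SAP 9.4, which confines counting once to per-participant incidence.
- For counting participants: the footnote alone, in words identical to those under the two participant tables just before it.

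**2. Does any other adverse event table count events?** Tables 14.3.1.1 to 14.3.1.9.2 count participants. SAP 9.4.3 describes Figure 14.3.1.11 as a frequency of events, but the figure is titled as a proportion of participants. Table 14.3.1.10 is the only candidate.

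**3. What does the footnote do to the numbers?** Take one participant who, in one period, has PT1 three times and PT2 once, both in the same SOC.

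| Row | All events | Under the footnote |
|---|---|---|
| PT1 | 3 | 1 |
| PT2 | 1 | 1 |
| SOC | 3 + 1 = 4 | 1 |

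The right-hand column is what Table 14.3.1.9.1 would show for the same period. The SOC row loses more than the PT rows, because different terms within one SOC also collapse to one.

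**4. How large could the loss be?** The documents give no repeat rate, so this is an illustration over an assumed range. Let events per participant for one PT in one period be Poisson with mean λ, and take n = 20 per group (SAP 4.1).
- Expected events: 20λ.
- Expected count under the footnote: 20(1 − e^(−λ)).
- Share removed: 1 − (1 − e^(−λ))/λ.
- Chance that at least one of 20 participants has a repeat: 1 − [(1 + λ)e^(−λ)]^20.

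| λ (assumed) | Events | Counted | Removed | Chance of any repeat |
|---|---|---|---|---|
| 0.1 | 2.0 | 1.90 | 4.8% | 9% |
| 0.25 | 5.0 | 4.42 | 11.5% | 42% |
| 0.5 | 10.0 | 7.87 | 21.3% | 85% |
| 1.0 | 20.0 | 12.64 | 36.8% | over 99% |

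The error can only be downward. Where no participant repeats a term, the PT rows are unaffected.

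**5. Where else would a non-serious Grade 4 event appear?**
- Table 14.3.1.1, in the row for Grade 2 or greater unsolicited events.
- The Table 14.3.1.7 shell, which has a life-threatening row.
- If it is a laboratory value, Table 14.3.4.1, which has Grade 4 columns for every parameter except albumin.
- If it is a laboratory value, Table 14.3.4.4, which under SAP 9.7 lists every result of Grade 1 or higher.
- Listing 16.2.7.2, which holds all unsolicited events.

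**The case against.** The strongest reply is that this is a carried-over footnote and not a decision about the analysis. Four instructions point to events and one to participants, so a careful programmer would probably count events. That is the likeliest explanation, and it is why the point is minor. It does not remove the point: a shell footnote is a direct programming instruction, and the table would be wrong if it were followed.

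It can also be said that repeats are foreseen elsewhere. The Table 14.3.1.7 shell carries a sample footnote stating that no participant had the same event twice, and Listing 16.2.7.2 shows each event. Both are true. But the first is sample text and not a count, and the second is a listing and not a summary.

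On Table 14.3.2.2, a reader might infer that a non-serious Grade 4 event would be in neither that listing nor Table 14.3.2.1, and that the tables under-report the highest grades. The documents do not support this. The text of SAP 9.4.3 already says moderate or greater. Table 14.3.2.1 is titled to include other significant events as well as deaths and serious events. SAP 9.5 describes its content only as deaths and serious events, and significant is undefined, so inclusion there is not assured, but exclusion is not stated either. The outputs in step 5 would show such an event in any case. The exposed set is also narrow: clinical events with immediate risk of death are serious by definition, scheduled post-vaccination safety bloods are drawn once, at Day 8, and the missing-severity rule in SAP 6.5 treats Grade 3 as the maximum for an event not captured as serious.

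**Conclusion.** The footnote of Table 14.3.1.10 contradicts the table's title, its column heads and SAP 9.4.3. Followed as written, it turns the plan's only event count into a second copy of the participant counts in Table 14.3.1.9.1. This rests on the texts alone. The size depends on the unknown repeat rate: 4.8% to 36.8% of events of a term over the assumed range of 0.1 to 1.0 events per participant, and nothing in the PT rows if no participant repeats a term.

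The consequence is limited. The Protocol 7.3.1 safety summaries are numbers and percentages of participants, and no endpoint, interval or pause rule uses this table. It would go too far to say that events are lost from the report, because Listing 16.2.7.2 keeps every unsolicited event. The Table 14.3.2.2 matter is a title that should be aligned with its text, and no more.

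**What to change.** 1. Delete the once-per-participant sentence from the footnote of Table 14.3.1.10 and state that every event is counted. Keep the sentence under Tables 14.3.1.9.1 and 14.3.1.9.2.
2. Retitle Table 14.3.2.2 *Moderate or Greater*, so that it matches SAP 9.4.3 and clearly includes non-serious Grade 4 events.
3. While the Table 14.3.1.10 shell is open, correct its second period. It is headed as Day 8 onward, which overlaps with Days 1-8, whereas SAP 9.4.3 has the second period start after Day 8.

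The cost is three small shell edits before programming. No data collection, sample size or analysis method changes.

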### FIGURE 14.3.1.11.2:

Proportion of Participants with Unsolicited, Non-Serious Adverse Events, by MedDRA® System
Organ Class and Maximum Severity per Participant - Full Analysis Population
- Non-Adjuvanted MCV-5

### FIGURE 14.3.1.11.3:

Proportion of Participants with Unsolicited, Non-Serious Adverse Events, by MedDRA® System
Organ Class and Maximum Severity per Participant - Full Analysis Population
- Menactra®

### 14.3.2 AE and SAE Listings

### TABLE 14.3.2.1: Listing of Deaths, Serious Adverse Events and Other Significant Events

Participant ID	Treatment Group	Adverse Event description	AE Start Date	# of Days Post Dose	Severity	Outcome	Resolution Date / Ongoing	Duration (Days)	Reasonable possibility that the study product caused the event?

### (continued)

Participant ID	Adverse Event description	MedDRA® System Organ Class	MedDRA® Preferred Term	SAE / If Yes, Reason Reported as an SAE	Event Evaluated for Halting Criteria?	Comments

### TABLE 14.3.2.2: Listing of Non-Serious, Unsolicited, Moderate or Severe Adverse Events

Participant ID	Treatment Group	Adverse Event	Start Date	# of Days Post Dose	Severity	Outcome	Resolution Date / Ongoing	Duration (Days)	Reasonable possibility that the study product caused the event?

### (continued)

Participant ID	Adverse Event description	MedDRA® System Organ Class	MedDRA® Preferred Term	SAE / If Yes, Reason Reported as an SAE	Event Evaluated for Halting Criteria?	Comments

### 14.3.3 Narratives of Deaths, Other Serious and Significant Adverse Events

[This is a place holder for this section in the CSR.]

TABLE 14.3.4.1: Laboratory Results by Parameter, Maximum Severity, Study Day, and Treatment Group - Full Analysis Population

		None	Mild / Grade 1	Moderate / Grade 2	Severe / Grade 3	Life-Threatening / Grade 4	Missing
Treatment Group	N	n (%)	n (%)	n (%)	n (%)	n (%)	n (%)
Baseline							
Adjuvanted MCV-5	Х	x (xx.x)	x (xx.x)	x (xx.x)	x (xx.x)	x (xx.x)	x (xx.x)
Non-Adjuvanted MCV-5	Х						
Menactra ®	X						
Day 8						 	
Adjuvanted MCV-5	X						
Non-Adjuvanted MCV-5	х						
Menactra ®	х						
Maximum Severity Post-I	Baselin	ne 				 	
Adjuvanted MCV-5	X						
Non-Adjuvanted MCV-5	х						
Menactra ®	х						

<sup>1 Includes values collected at unscheduled visits.

Table 14.3.4.1: Laboratory Results by Parameter, Maximum Severity, Study Day and Treatment Group - Full Analysis Population (Continued)

### Hemoglobin (g/dL)

			None		Mild/ Grade 1 (Low)		Moderate/ Grade 2 (Low)		Severe/ Grade 3 (Low)		Life-Threatening/ Grade 4 (Low)		Mis	ssing
Time Point	Treatment Group	N	n	n %		%	n	%	n	%	n	%	n	%
Baseline	Adjuvanted MCV-5	X	х	X.X	X	X.X	X	X.X	X	X.X	X	X.X	X	x.x
	Non-Adjuvanted MCV-5	Х	х	X.X	X	X.X	Х	X.X	X	X.X	Х	X.X	X	X.X
	Menactra ®	Х	х	X.X	X	X.X	Х	X.X	X	X.X	Х	X.X	X	X.X
Day 8	Adjuvanted MCV-5	Х	х	X.X	X	X.X	X	x.x	X	X.X	Х	X.X	X	X.X
	Non-Adjuvanted MCV-5	Х	х	X.X	X	X.X	X	X.X	X	X.X	X	X.X	X	x.x
	Menactra ®	х	х	X.X	X	X.X	Х	X.X	Х	X.X	Х	X.X	X	x.x
Max Severity Post Baseline 	Adjuvanted MCV-5	Х	х	X.X	X	X.X	X	x.x	X	X.X	Х	X.X	X	X.X
	Non-Adjuvanted MCV-5	х	х	X.X	X	x.x	X	x.x	Х	X.X	Х	X.X	Х	X.X
	Menactra®	X	х	x.x	X	x.x	Х	x.x	х	x.x	х	X.X	X	x.x

<sup>1 Includes values collected at unscheduled visits.

Table 14.3.4.1: Laboratory Results by Parameter, Maximum Severity, Study Day and Treatment Group - Full Analysis Population (Continued)

### Platelet Counts (cells/mm^3)

			None		Mild/ Grade 1 (Low)		Moderate/ Grade 2 (Low)		Severe/ Grade 3 (Low)		Life-Threatening/ Grade 4 (Low)		Mis	ssing
Time Point	Treatment Group	N	n	n %		%	n	%	n	%	n	%	n	%
Baseline	Adjuvanted MCV-5	X	X	X.X	X	X.X	X	X.X	X	X.X	X	X.X	X	x.x
	Non-Adjuvanted MCV-5	х	Х	X.X	Х	X.X	Х	X.X	X	X.X	Х	X.X	X	X.X
	Menactra ®	х	Х	X.X	Х	X.X	Х	x.x	Х	X.X	Х	X.X	Х	X.X
Day 8	Adjuvanted MCV-5	х	Х	X.X	Х	X.X	X	x.x	X	x.x	Х	X.X	Х	X.X
	Non-Adjuvanted MCV-5	Х	Х	X.X	Х	X.X	X	x.x	X	X.X	Х	X.X	Х	x.x
	Menactra ®	х	Х	X.X	Х	X.X	Х	x.x	Х	X.X	Х	X.X	Х	X.X
Max Severity Post Baseline 	Adjuvanted MCV-5	х	Х	X.X	Х	X.X	X	x.x	X	X.X	Х	X.X	X	X.X
	Non-Adjuvanted MCV-5	х	х	X.X	Х	X.X	Х	x.x	X	x.x	Х	X.X	Х	X.X
	Menactra®	х	х	x.x	X	x.x	X	x.x	X	x.x	х	X.X	X	x.x

<sup>1 Includes values collected at unscheduled visits.

Table 14.3.4.1: Laboratory Results by Parameter, Maximum Severity, Study Day and Treatment Group - Full Analysis Population (Continued)

### White Blood Cells (cells/mm^3)

			None		Mild/ Grade 1		Moderate/ Grade 2		Severe/ Grade 3		Life-Threatening/ Grade 4		Missing	
Time Point	Treatment Group	N	n	%	n	%	n	%	n	%	n	%	n	%
Baseline	Adjuvanted MCV-5	X	X	x.x	X	x.x	X	X.X	X	x.x	X	X.X	X	x.x
	Non-Adjuvanted MCV-5	X	X	x.x	X	x.x	X	X.X	X	x.x	X	X.X	X	x.x
	Menactra®	X	X	x.x	X	x.x	X	x.x	X	X.X	X	x.x	X	x.x
Day 8	Adjuvanted MCV-5	х	Х	x.x	X	X.X	Х	X.X	X	X.X	Х	X.X	х	X.X
	Non-Adjuvanted MCV-5	X	X	x.x	X	x.x	X	x.x	X	X.X	X	x.x	X	x.x
	Menactra®	х	Х	x.x	X	X.X	Х	X.X	X	X.X	Х	X.X	х	X.X
Max Severity Post Baseline 	Adjuvanted MCV-5	х	х	X.X	X	X.X	Х	X.X	Х	X.X	х	X.X	X	X.X
	Non-Adjuvanted MCV-5	х	х	x.x	Х	X.X	Х	X.X	X	X.X	х	X.X	х	X.X
	Menactra®	х	X	x.x	X	x.x	X	X.X	X	x.x	Х	X.X	X	x.x

<sup>1 Includes values collected at unscheduled visits.

Table 14.3.4.1: Laboratory Results by Parameter, Maximum Severity, Study Day and Treatment Group - Full Analysis Population (Continued)

### Alanine Aminotransferase (ALT) (U/L)

			None		Mild/ Grade 1 (High)		Moderate/ Grade 2 (High)		Severe/ Grade 3 (High)		Life Threatening/ Grade 4 (High)		Missing	
Time Point	Treatment Group	N	n	%	n	%	n	%	n	%	n	%	n	%
Baseline	Adjuvanted MCV-5	X	X	X.X	X	X.X	X	X.X	X	x.x	х	x.x	X	X.X
	Non-Adjuvanted MCV-5	Х	X	X.X	X	X.X	Х	X.X	Х	X.X	X	X.X	Х	X.X
	Menactra®	Х	Х	X.X	Х	X.X	х	X.X	Х	X.X	Х	X.X	Х	X.X
Day 8	Adjuvanted MCV-5	х	Х	X.X	Х	X.X	х	X.X	Х	X.X	Х	X.X	х	x.x
	Non-Adjuvanted MCV-5	Х	X	X.X	Х	X.X	Х	X.X	Х	x.x	х	x.x	Х	X.X
	Menactra®	Х	X	X.X	X	X.X	Х	X.X	Х	X.X	X	X.X	Х	X.X
Max Severity Post Baseline 	Adjuvanted MCV-5	X	X	X.X	X	X.X	Х	X.X	Х	X.X	X	X.X	Х	X.X
	Non-Adjuvanted MCV-5	Х	X	X.X	Х	X.X	Х	X.X	X	X.X	X	X.X	Х	X.X
	Menactra ®	X	X	x.x	X	x.x	х	x.x	X	X.X	X	X.X	X	x.x

<sup>1 Includes values collected at unscheduled visits.

Table 14.3.4.1: Laboratory Results by Parameter, Maximum Severity, Study Day and Treatment Group - Full Analysis Population (Continued)

### Creatinine (mg/dL)

			None		Mild/ Grade 1 (High)		Moderate/ Grade 2 (High)		Severe/ Grade 3 (High)		Life Threatening/ Grade 4 (High)		Missing	
Time Point	Treatment Group	N	n	%	n	%	n	%	n	%	n	%	n	%
Baseline	Adjuvanted MCV-5	X	X	X.X	X	X.X	X	X.X	X	X.X	X	x.x	X	X.X
	Non-Adjuvanted MCV-5	X	х	X.X	X	X.X	X	X.X	X	X.X	X	x.x	X	X.X
	Menactra ®	X	х	X.X	X	X.X	X	X.X	X	X.X	X	x.x	X	X.X
Day 8	Adjuvanted MCV-5	х	х	X.X	х	X.X	X	X.X	X	X.X	X	x.x	Х	X.X
	Non-Adjuvanted MCV-5	х	х	X.X	х	X.X	X	X.X	X	X.X	X	x.x	Х	X.X
	Menactra ®	х	Х	X.X	х	X.X	Х	X.X	Х	X.X	Х	x.x	X	X.X
Max Severity Post Baseline 	Adjuvanted MCV-5	х	X	X.X	X	X.X	X	X.X	X	X.X	X	x.x	X	X.X
	Non-Adjuvanted MCV-5	х	х	X.X	X	X.X	Х	X.X	Х	X.X	X	x.x	Х	X.X
	Menactra ®	х	Х	x.x	х	x.x	X	x.x	X	x.x	Х	X.X	X	x.x

<sup>1 Includes values collected at unscheduled visits.

Table 14.3.4.1: Laboratory Results by Parameter, Maximum Severity, Study Day and Treatment Group - Full Analysis Population (Continued)

